9.2.1 Process for recording adverse events

All adverse events will be recorded (across both arms) by researchers when they are made aware of the event by the patient, carer, the treating clinicians, or therapists, in accordance with the principles of 'Good Clinical Practice'. Adverse event reporting information will be included in the training given to the therapy teams delivering the intervention and they will be given Instructions on how to enter adverse events on to the trial database. The adverse event form will be completed by investigators at site who will complete information including the seriousness of the event and whether it is related to the intervention. All adverse events will be presented to the Independent Data and Safety Monitoring Committee (IDSMC) periodically. Trial- serious related events will be reported to the CTRC within 24 hours of sites becoming aware. They will also be reported to the IDSMC Chair person and the research ethics committee periodically.

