10 SAFETY REPORTING

All safety events will be recorded by researchers when they are made aware of the event by the patient, carer, the treating clinicians, or therapists, in accordance with the principles of GCP. Safety event reporting information will be included in the training given to the therapy teams delivering the intervention and they will be given copies of the safety event reporting forms and details of how to enter them on to the trial database or send to the CTRC.

AE reports and SAEs not related to the intervention will be entered on to the remote data entry system at follow-up visits. SAE reports related to the intervention will be completed and sent to the CTRC within 24 hours of becoming aware of the event.

Safety events will be captured on two separate forms: Adverse Events form for all non-serious events and SAEs not related to intervention and a Serious Adverse Events (SAE) form for serious events related to intervention. The SAE form will have two sections, the first is for the healthcare professional to complete at site who will complete information including the seriousness of the event and whether it is related to the trial and return to the CTRC trial manager. The trial manager will liaise with the Chief Investigator (or agreed delegate) who will complete the second part of the form, including an assessment of expectedness for related events.

All SAEs, along with the PI's assessment of whether it is related to the intervention and for related events the CI's assessment of whether or not it is expected, will be reported to the REC annually. All SAEs which are assessed as related and unexpected will be reported to the REC and Sponsor in an expedited manner.

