10.1 Definitions

There are different categories of safety events.

Adverse Event (AE)

An "Adverse Event" (AE) is any untoward medical occurrence in a participant, including events which are not necessarily caused by or related to the trial intervention. See section 10.2 for further guidance.

Related Adverse Event (related AE)

A "Related Adverse Event" (related AE) is an AE which has been assessed as having a causal relationship to the trial intervention (see section 10.5 below).

Serious Adverse Event (SAE)

A "Serious Adverse Event" is an AE which has been assessed as meeting the definition of "serious" (see section 10.3 below).

Related Serious Adverse Event (related SAE)

A "Related Serious Adverse Event" is an SAE which has been assessed as having a causal relationship to the study intervention (see section 10.5 below).

Related Unexpected Serious Adverse Event (RUSAE)

A "Related Unexpected Serious Adverse Event" is a related SAE which has been assessed as being unexpected (see section 10.6 below).

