10.6 Assessing "expectedness"

The assessment of expectedness will be performed by the Chief Investigator (or agreed delegate), not by the site research team.

All safety events assessed as "serious" and "related" will be assessed as expected and classified as RUSAEs if they meet the following criteria:

- Repeat fall during therapy sessions
- Repeat fracture during therapy sessions
- Other accident of injury during therapy sessions

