10.8.2 Serious safety events (SAEs / related SAEs / RUSAEs)

All serious events related to intervention, and whether expected or not should be recorded on an SAE form. The SAE form asks for the nature of event, date of onset, severity, corrective therapies given, outcome and causality. The responsible investigator should sign the causality of the event.

SAEs **related** to the intervention (related SAEs / RUSAEs) should be reported to the CTRC within 24 hours of the local site becoming aware of the event. SAEs that are **not related** to the intervention (SAEs) should be entered into the trial database at 17 or 52 weeks.

Local Principal Investigators should report any SAEs as required locally.

All serious events (SAEs / related SAEs / RUSAEs) will be reported annually to the REC and periodically to the IDSMC by the CTRC. Unexpected, related and serious events (RUSAEs) will also be reported in an expedited manner (15 days from CTRC being aware) to REC.

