15.3.3 Independent Data and Safety Monitoring Committee (IDSMC)

The independent Data and Safety Monitoring Committee (IDSMC) consists of an independent chairperson, plus 2 independent members who are experts in the field of hip fractures and rehabilitation.

The IDSMC will be responsible for reviewing and assessing recruitment, interim monitoring of safety and effectiveness, trial conduct and external data. The IDSMC will first convene prior to the start of recruitment and will then define frequency of subsequent meetings (at least annually). Details of the interim analysis and monitoring are provided in section 11 and 13.

The IDSMC will provide a recommendation to the TSC concerning the continuation of the trial. Refer to the IDSMC charter and trial oversight committee membership document for further details.

Name	Affiliations	Contribution to protocol
[name]	Department of Health Services Research, University of Liverpool	Chief Investigator
[name]	Clinical Trials Research Centre University of Liverpool Institute of Child Health Alder Hey Children's NHS Foundation Trust Liverpool	Head of Trial Management
[name]	Clinical Trials Research Centre University of Liverpool Institute of Child Health Alder Hey Children's NHS Foundation Trust Liverpool	Supervising Trial Manager
[name]	Clinical Trials Research Centre University of Liverpool Institute of Child Health Alder Hey Children's NHS Foundation Trust Liverpool	Senior Statistician
[name]	Clinical Trials Research Centre University of Liverpool Institute of Child Health Alder Hey Children's NHS Foundation Trust Liverpool	Senior Data Manager
[name]	Clinical Trials Research Centre University of Liverpool Institute of Child Health Alder Hey Children's NHS Foundation Trust Liverpool	Trial Co-ordinator
[name]	Site for Health Economics and	Health Economist

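### Section 10.6 classes the listed therapy-session events as both expected and RUSAEs, against the section 10.1 definition, and so can misroute expedited safety reports

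*Protocol*

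**What the plan says.** Five places in the protocol bear on this.

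- **Section 10.1** defines the term: a RUSAE "is a related SAE which has been assessed as being unexpected".
- **Section 10.6** gives the Chief Investigator, or an agreed delegate, the task of judging expectedness. It says that events already judged serious and related "will be assessed as expected and classified as RUSAEs if they meet the following criteria". The list has three entries: a repeat fall, a repeat fracture, and another accident or injury, each in a therapy session.
- **Section 10** sets the expedited route by its attributes: "All SAEs which are assessed as related and unexpected will be reported to the REC and Sponsor in an expedited manner".
- **Section 10.8.2** sets the time limit: "Unexpected, related and serious events (RUSAEs) will also be reported in an expedited manner (15 days from CTRC being aware) to REC". It does not name the Sponsor. It also says that all serious events, RUSAEs included, "will be reported annually to the REC and periodically to the IDSMC by the CTRC".
- **Section 9.2.1** says of related serious events: "They will also be reported to the IDSMC Chair person and the research ethics committee periodically".

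**The concern.** Sections 10.1 and 10.6 cannot both be applied. In section 10.1 unexpectedness is what makes a related SAE a RUSAE. In section 10.6 the listed events are called expected and are made RUSAEs in the same sentence.

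This matters because the label decides who hears of a related serious event, and when. A RUSAE is due at the REC within 15 days of CTRC awareness and goes expedited to the Sponsor. A related SAE that is not a RUSAE is due at the REC only in the annual report. The listed events are also close to the one hazard of the intervention that section 3.2.5 names, injury or falling during the exercises. So the rule is faulty for the events the trial most plausibly expects. For events nobody foresaw, which expedited reporting exists to catch, it gives no instruction.

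**Working it through.** No arithmetic applies. The check takes the two kinds of related SAE and follows each under the two sections.

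| Related SAE | Section 10.1, with the list read as expected events | Section 10.6 taken literally |
|---|---|---|
| On the list (for example, a fall with fracture in a therapy session) | Expected, so not a RUSAE. REC: annual report. Sponsor: no expedited report. | Classified as a RUSAE. REC: 15 days. Sponsor: expedited. |
| Not on the list | Unexpected if so assessed, hence a RUSAE. REC: 15 days. Sponsor: expedited. | Not in the only class that section 10.6 calls RUSAEs. No rule is given, and the event might get the annual report alone. |

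Three things follow.

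1. **The routes swap.** For the first row the two sections give opposite answers. For the second row, section 10.1 leads to the expedited route, while section 10.6 never says that an unlisted event is unexpected.
2. **The second row can occur.** As an illustration, take a participant who fractures a bone while practising workbook exercises alone at home. Section 12.2 confirms that the workbook contains such exercises. The event could be judged serious and related, but it did not happen in a therapy session, so it is off the list.
3. **IDSMC timing is the same in all four cells.** Under either reading, section 10.8.2 sends serious events to the IDSMC periodically. The contradiction affects only the REC and the Sponsor.

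The recipients differ as well. Section 10 names the REC and the Sponsor for expedited reports. Section 10.8.2, the only place with the 15-day limit, names the REC alone, so no time limit is attached to the Sponsor's copy.

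**The case against.** The best defence is that this is a drafting slip with a clear intention behind it. Sections 10, 10.1 and 10.8.2 all tie expediting to unexpectedness, so section 10.6 is outvoted. One central assessor applies the rule, which limits inconsistency between sites. Related SAEs reach the CTRC within 24 hours whatever their label, and every serious event appears in the annual REC report, so nothing is lost altogether. The protocol also describes the intervention as low risk.

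Most of this stands, and it limits the consequence. It does not remove the defect. Section 10.6 is the only place with an operative list, and the assessor has to work from it. Nor is it certain which word is wrong: the sentence makes sense either if the events are expected and not RUSAEs, or if they are unexpected and RUSAEs. A single assessor using the wrong reading would misroute every such event consistently.

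A reader might infer two stronger points, and the protocol supports neither.

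- *That the IDSMC would learn of related serious events too late, because no interval is set.* The protocol states no expedited route to the IDSMC or its Chair. However, section 15.3.3 has the committee convene before recruitment and set its own meeting frequency, at least annually, and refers to a charter that is not shown. Leaving such timing to a charter is normal practice. No delay is demonstrated, and copying every related SAE to the Chair by a fixed day is a preference.
- *That section 9.2.1 conflicts with section 10.8.2 on REC timing.* An annual report is a periodic one, and section 10.8.2 says that RUSAEs are also expedited. The two statements are compatible.

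**Conclusion.** Section 10.6 is wrong as written and should be corrected. It contradicts the definition in section 10.1 on the property that decides expedited reporting.

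The size can be given only as a difference in route. For the REC, an affected event would be due either 15 days after CTRC awareness or at the next annual report. For the Sponsor, it would be either expedited or not. The number of such events cannot be estimated, because the protocol gives no related-SAE rate. Nor do the documents support converting recruitment speed into a count of participants exposed, since no reporting lag is known.

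The conclusion rests on the text alone, with one assumption: that the list is meant to name expected events. The section's purpose and the risk named in section 3.2.5 make that the likelier intention, but the sponsor should confirm it. The contradiction stands whichever was meant. The missing Sponsor in section 10.8.2 is a smaller inconsistency that belongs in the same correction.

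**What to change.** **Section 10.6.** Replace the classifying sentence with wording such as: *Related SAEs on the list below are assessed as expected. Every other related SAE is assessed as unexpected and classified as a RUSAE.* If the sponsor wants therapy-session falls and fractures expedited despite being expected, it should state that as a separate reporting rule and leave the RUSAE definition intact.

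**Section 10.8.2.** Name the Sponsor beside the REC in the expedited-reporting sentence, to match section 10.

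**Optional.** Cross-refer section 9.2.1 to section 10.8.2 for REC timing. If the IDSMC charter contains an expedited route to the Chair, cite it in section 10.8.2.

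The cost is two corrected sentences in the next amendment and a short note to the assessor of expectedness. No new data, staff or committee is needed. If any related SAE has already been assessed, its classification should be checked against the corrected rule.

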9.3 Other Assessments

9.3.1 Health Economic Analysis

The enhanced rehabilitation programme will be fully costed (e.g., salary band of therapists, time spent with the patient conducting rehabilitation, costs of travel and costs of any additional equipment) from a public sector multiagency perspective including health and social care. Unit costs will be obtained from national sources of reference costs. Costs of health and social care services used by the participants will also be costed using national sources of reference costs ^{44,45}. The costs of service use and the cost of the intervention will be added together for use in a cost-utility analysis.

The EQ-5D -3L will be used to calculate QALYs over the 52-week trial period, using area under the curve method ⁴¹. QALYs measure health gain by aggregating the number of years gained from a drug or health care intervention, weighted by the proportion that represents the relative value attached to a given health state (utility) ⁵².

A cost-utility analysis will be conducted to calculate a cost per QALY of the enhanced rehabilitation intervention. Differences in mean QALYs and service use costs between the groups will be calculated, and 95% Confidence Intervals around these differences produced. This cost per QALY generated will be compared to the NICE threshold range of £20,000 to £30,000 per QALY ⁵³. We will bootstrap differences in costs and outcomes (EQ-5D 3L) between the two groups, producing a 95% confidence interval around these differences.

9.3.2 **Process Evaluation**

The process evaluation of the FEMuR III trial will aim to examine the mechanisms and processes (i.e. the intervention theory) that explain the implementation and impacts of the enhanced rehabilitation programme. The process evaluation will help build a picture of how the FEMuR proposed programme is carried out in reality, and what factors shaped it. By carrying out a process evaluation it will be possible to identify if observed impacts are solely due to the enhanced rehabilitation programme, or if these impacts are a result of a number of external and internal variables that are closely linked to the environment and the context in which the programme takes place ⁵⁶⁻⁵⁹.

The specific objectives will be to:

- Refine the programme theory that was generated from the previous realist review when developing the intervention programme (MRC framework phase I). This will explain how the FEMuR enhanced rehabilitation programme is expected to work to generate outcomes amongst a complex patient group. This programme theory will also explain how the researchers envisage the intervention to reach its expected outcomes via identifying a set of tangible assumptions that will further be used to guide the analysis and synthesis of data.
- Investigate therapists' expectations and experience of implementation, identifying the actual practices, likely tailoring and interactions that took place within the trial setting. Also, investigate therapists' skill level, relevant training, previous experience and level of familiarity of working in this sector. Finally, investigate therapists learning over time and its potential impact on outcomes.
- Investigate the mechanisms driving and shaping the tailoring of the enhanced rehabilitation programme to individual patients and its possible impacts on outcomes.
- Investigate trial participants' experiences and views about their involvement in the FEMuR trial.
- Synthesise all data collected and link it to the explanation of trial findings in relation to the refined programme theory.

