The economic evaluation used a cost consequence analysis. The cost of delivering the intervention was £231 per patient. Both the intervention and control groups showed improvements in EQ-5D health utility index scores and the ICECAP capability index scores from baseline to the three-month follow-up. The differences between groups were not statistically significant, but this small feasibility trial was not powered to test such differences. The intervention group had slightly higher mean QALY gains than the control group, which were not statistically significant either. The difference in QALY was 0.02 (95% CI -0.02 to 0.06). There was however, a statistically significant difference in hospital costs between the groups due to longer inpatient stays in one group. The mean total service use costs were £43 999 higher in the intervention group (95% CI £4 027 to £88 818).

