8.3 Enhanced rehabilitation

The main aim of the intervention is to enhance usual rehabilitation by enhancing patients' selfefficacy, and increasing the amount and quality of patients' practice of physical exercise and activities of daily living in order to improve their functional outcomes at 17 and 52 week follow up ²⁴. Self-efficacy will be enhanced by means of a patient held information workbook and diary given to the participant in the acute hospital and kept with them throughout the follow up period of the trial. In addition to whatever community based rehabilitation is provided as part of usual care, we will provide up to six additional therapist (physiotherapist or occupational therapist) or technical instructor sessions to patients once they either return home or are admitted permanently to a care home. The extra sessions will be tailored by the therapists delivering them, and so the total number of sessions used, the time scale for their delivery, and the sessions' content will vary between patients according to clinical need.

The workbook will also include information about what to expect from their recovery and information about NHS, council and voluntary sector services they may be able to use. This will include a variety of community services such as falls preventions programmes. The objectives of the workbook and diary are to:

- 1) Give patients better understanding of what has happened physically to them and to broadly outline what to expect during their recovery.
- 2) Provide information and contact details on rehabilitation services that are available to them as they progress in their rehabilitation (e.g. Intermediate care teams, social services enablement teams, outpatient physiotherapy, falls prevention groups, national exercise referral services). The information will enable patients to ask the therapist they are working with or their GP about available services and what benefit they might offer, and at what stages they would be most beneficial, and to contact the services themselves for more information.
- 3) To enable them to work collaboratively with their therapist to set goals and monitor progress of their rehabilitation in order to improve the quality and the quantity of the physical and activities of daily living exercises they are performing.
- 4) To improve patients' self-efficacy
 - a. To encourage the patient to set goals they want to achieve and to discuss them with their therapist.

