- If the session was face to face, how much time was spent on different aspects such as, physical exercises, activities of daily living (ADL) practice, working on the workbook
- When the sessions were given in patient's recovery timeline

Data from these records will be used to monitor participant adherence (e.g. missed or cancelled appointments), and therapist adherence to the trial protocol. In addition, as part of the health economic data collection we will ask all patient participants to record health service and admissions data along with concomitant medication use on the CSRI collected at baseline and at 17 and 52 weeks' follow-up.

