This is a short series of physical function tests which assess lower limb function in terms of balance, gait, strength and endurance. The tests involve: examining the ability to stand with feet together in the side-by-side, semi-tandem and tandem positions; measuring the time to walk 8 feet (2.5m) and the time to rise from a chair and return to the seated position five times. Each test and a summary performance scale obtained by summing the categorical ranking on each test (0-12) were strongly associated with self-reported disability and were independent predictors of short-term mortality and nursing home admission. This was found even at the high end of the functional spectrum in those reporting almost no disability. This battery of tests was designed for use in people's homes and will be administered by the researcher at the 17 and 52 week follow-up assessments.

Health economic measures

EuroQol EQ-5D-3L (three levels)⁴¹

This is a patient-completed index of health-related quality of life, which gives a weight to different health states. It consists of five dimensions: mobility, self-care, usual activities, pain/discomfort, and anxiety/depression. Each has three possible responses. The responses record three levels of severity (no problems, /moderate problems, or severe problems) which is then converted to a health utility weight using UK norms. It also has a VAS ranging from 0 to 100 where the participant draws a line on the scale to rate their health state today. It will be used at baseline and at the 17 and 52 week follow-up assessments, and allows the calculation of quality-adjusted life years (QALY) using the area under the curve method which will be used as part of the economic analysis⁴².

Client service receipt inventory (CSRI)⁴³

The CSRI is a questionnaire for collecting retrospective information about trial participants' use of health and social care services, including voluntary services (e.g. charity services) and the components of the rehabilitation programme. This information will be combined with national sources of reference unit costs^{44,45} in order to calculate health and social care service costs for the economic evaluation. It will be used at baseline and at the 17 and 52 week follow-up assessments as part of the economic analysis. A reduced version of the CSRI will be used at baseline to reduce participant burden as participants are recovering from hip fracture surgery.

Carer completed measure - secondary outcome

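### The intervention cost is added to a service-use cost that may already contain the trial-provided sessions, so these may be counted twice, in the intervention arm only

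*Protocol*

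**What the plan says.** Section 9.3.1 builds the cost side of the cost-utility analysis from two lines.

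- **Intervention line.** "The enhanced rehabilitation programme will be fully costed (e.g., salary band of therapists, time spent with the patient conducting rehabilitation, costs of travel" and any extra equipment are the stated inputs.
- **Service-use line.** "Costs of health and social care services used by the participants will also be costed using national sources of reference costs".

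The two are then summed: "The costs of service use and the cost of the intervention will be added together for use in a cost-utility analysis".

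Section 11.5 says what feeds the service-use line. The CSRI collects use of health and social care services, "including voluntary services (e.g. charity services) and the components of the rehabilitation programme", and its content is combined with unit costs "in order to calculate health and social care service costs for the economic evaluation". Section 9.3.2.1 confirms that both arms complete it: "as part of the health economic data collection we will ask all patient participants to record health service and admissions data".

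The sessions at issue are described in section 8.3: "we will provide up to six additional therapist (physiotherapist or occupational therapist) or technical instructor sessions", on top of whatever usual community rehabilitation is given. Section 9.3.2.1 has the visiting therapist log each extra session on a case report form. Usual rehabilitation is recorded separately, in patient-held diaries that therapists fill in.

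**The concern.** The two cost lines overlap as described. A trial-provided visit uses therapist time and travel, so it belongs to the intervention line. It is also a contact with a community therapist and a part of a rehabilitation programme, so it fits the description of what the CSRI collects. The protocol gives no rule that assigns it to one line only.

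Only intervention patients receive these visits and only they have an intervention cost line. Any duplication would therefore add to one arm's cost. It would not cancel in the comparison, and a larger sample would not dilute it.

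Separating the visits at interview is not straightforward. Section 8.6 has outcomes collected by an assessor blind to allocation, who asks participants beforehand not to reveal their arm. That assessor cannot readily ask which visits were trial sessions.

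The cost-utility comparison is the first secondary objective (section 3.3.2) and is judged against £20,000 to £30,000 per QALY, so a one-sided cost error bears on a stated conclusion of the trial.

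**Working it through.** The protocol states no cost per QALY for this trial, so there is no figure to reproduce. The check is of the costing rule, followed by an illustration of scale.

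**Step 1: the rule in symbols.** Let U be the cost of services other than trial sessions, C the intervention cost per patient, and f the amount of trial-session cost that also enters through the CSRI, as a share of C.

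- Intended total, intervention arm: U + C
- Total under the stated rule: (U + f × C) + C = U + (1 + f) × C
- Control arm under either: U, with no trial sessions and no intervention line
- Error in incremental cost: f × C

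The error is zero only if f = 0, that is, if the CSRI leaves trial sessions out or they are removed before the sum. The protocol states neither.

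**Step 2: inputs for scale.** From section 3.2.3.1: "The cost of delivering the intervention was £231 per patient", and a QALY difference of 0.02 (95% CI -0.02 to 0.06). The share f is not in the documents. I take 0 to 1 as an assumed range, with duplicated contacts priced at about the same unit cost as the delivery cost.

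**Step 3: incremental cost (no QALY assumption needed).**

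- f = 0.25: 0.25 × £231 = about £58 per intervention patient
- f = 0.5: 0.5 × £231 = about £116
- f = 1: £231

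In QALY terms, £231 equals 231/20,000 = 0.0116 QALY, or 231/30,000 = 0.0077 QALY.

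**Step 4: cost per QALY (illustration only).** The amount added by duplication is 231 × f / ΔQALY.

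| f | ΔQALY | Added £ per QALY |
|---|---|---|
| 0.25 | 0.02 | 2,888 |
| 0.5 | 0.02 | 5,775 |
| 1 | 0.02 | 11,550 |
| 1 | 0.01 | 23,100 |
| 1 | 0.04 | 5,775 |
| 1 | 0.06 | 3,850 |

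At ΔQALY = 0.02 the intervention cost alone contributes 231/0.02 = £11,550 per QALY counted once and 462/0.02 = £23,100 counted fully twice. It reaches £20,000 when f = (20,000 × 0.02)/231 - 1 = 0.73. At a QALY difference of zero or below, the ratio cannot be read this way.

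**Step 5: can the overlap be removed?** Suppose a patient reports T therapy contacts on the CSRI, of which r are trial sessions, and the therapist logged L trial sessions, with r no greater than L. The usual contacts reported are T - r. Subtracting all L, but not below zero, gives a count at or below T - r. Subtracting none gives T, which is at or above it. The two analyses therefore bracket the reported usual contacts.

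**The case against.** **The key phrase is undefined.** Section 11.5 refers to the rehabilitation programme without saying enhanced, and section 9.3.2.1 once calls NHS care the usual rehabilitation programme. If 11.5 means usual care only, the literal overlap weakens. The risk remains, because trial sessions are still community therapist visits that a patient asked about service use could report.

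**The detail may sit elsewhere.** The CSRI is described as bespoke in section 2, its items are not shown, and an analysis plan could remove the overlap. This stands as a reason not to assert that duplication will occur. It does not dispose of the point, because the protocol itself states a summation rule and an instrument description that overlap. Also, section 11.3 requires the analysis plan only before data collection is complete, so it may come after many questionnaires have been filled in.

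**Patients may know which visits are extra.** They are unblinded and hold a workbook and diary. That is fair, and the share of trial visits reported on the CSRI is unknown.

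A reader might draw three stronger conclusions, which the documents do not support.

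- *The sessions are charged twice and the cost per QALY is overstated.* No section says so. It depends on the CSRI items, on patient reporting and on no removal at analysis. The effect on the ratio also needs a positive QALY difference, and the feasibility interval includes zero.
- *Duplication moves the result across £20,000.* That needs about 73% or more duplication, a QALY gain of 0.02 from a feasibility trial with three-month follow-up, and no other cost difference. Section 3.2.3.1 reports a service-cost difference of £43,999 (95% CI £4,027 to £88,818), beside which £231 is small.
- *Any change in usual visits is hidden.* It is not, because section 9.3.2.1 records usual rehabilitation separately in the therapist-completed diaries.

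**Conclusion.** The point holds as a risk that the protocol's wording creates. Sections 9.3.1 and 11.5, read together, allow the trial-provided sessions to enter both cost lines, in the intervention arm only, and no stated rule prevents it. Any duplication would overstate incremental cost.

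The size is unknown. On the feasibility delivery cost it would be about £231 per intervention patient under full duplication at a similar unit cost, and less under partial duplication. It could differ in either direction if the CSRI contacts are priced at other national unit costs. The cost-per-QALY figures show scale only. The primary outcome analysis is not affected. The change is worth making because the correction is cheap and the error, if it occurs, is one-sided.

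**What to change.** 1. **Section 9.3.1.** State that each trial-provided session is costed once, from the session case report form, and that service-use cost excludes those sessions.
2. **Where CSRI therapy contacts cannot be told apart.** Remove the sessions logged for the same period from that participant's physiotherapist, occupational therapist and technical instructor contacts, not below zero. Check the result against the therapist-completed diaries of usual care.
3. **Section 11.5.** Reword the CSRI description so that it covers usual rehabilitation services and excludes trial-provided sessions. Deleting the phrase outright could drop usual rehabilitation from the description.
4. **Sensitivity analysis.** Run one cost analysis with no removal.

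The cost is a few sentences and a linkage between records the trial already plans to hold. Removal can be done at analysis by trial number, so the blinded assessor need not ask about allocation. The drawback is that removing every logged session from a recall-based count takes out some genuine usual visits when a patient under-reported trial sessions, and this too falls on one arm. The analysis without removal bounds that error, as step 5 of the working shows.
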